7.5.1 Limits of Agreement

Limits of agreement between IOP measurements made using GAT and the ARGOS-IO system from V10 (day 240) through V11 (day 360) will be assessed. If multiple ARGOS-IO system measurements have been made at time points for which paired GAT/ARGOS-IO system measurements are to be compared, the mean of the replicate ARGOS-IO system measurements will be used for agreement evaluation. The agreement evaluation is based on the assumption, that the measurements are constant over the measurement period.

The Bland-Altman method will be used to determine the upper and lower limits of agreement expected to contain 95% of the IOP value pairs obtained with the ARGOS-IO system and GAT. The two-sided 95% confidence intervals for each of these limits will be calculated using the Mover method (Zou, 2011) to account for repeated observations. IOP values will be displayed as Bland-Altman plots of individual measurement pairs by measurement technique for each individual participant as well as mean plots over time (per visit and overall).

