- Incidence, nature, severity and seriousness of observed adverse events and adverse device events in the 6 months following implantation.
- Incidence, nature, severity and seriousness of observed adverse events and adverse device events in the 12 months following implantation.

Performance

- Limits of agreement between measurements made using GAT and the ARGOS-IO system from V05 (day 30) through V11 (day 360).
- Performance of the ARGOS-IO system after 6 months by means of incidence of observed device malfunctions.
- Performance of the ARGOS-IO system after 12 months by means of incidence of observed device malfunctions.
- User acceptance of the implantation procedure by means of evaluation of implantation procedure questionnaires (investigators).
- User acceptance of the ARGOS-IO system at the investigational site by means of evaluation of investigator acceptance questionnaires (investigators).
- User acceptance of the ARGOS-IO system at home by means of evaluation of patient acceptance questionnaires (patients).
- Daily IOP self-measurement profiles (patients).

Definition of the analysis populations

The safety population comprises all subjects for whom ARGOS-IO pressure sensor implantation was attempted, whether or not the implantation was successful. In this clinical investigation the intention-to-treat (ITT) population comprises the same subjects as defined in the safety population.

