8.1.3.2 Secondary endpoints

Safety

- Incidence, nature, seriousness, severity and duration of adverse events and adverse device events in the 3 months immediately following implantation of the ARGOS-IO pressure sensor.
- Incidence, nature, seriousness, severity and duration of adverse events and adverse device events in the first 6 months following implantation of the ARGOS-IO pressure sensor

 Impladata Ophthalmic Products GmbH	Clinical Investigation Plan ARGOS-02	Revision C <hr/> Page 61 of 106
---	---	------------------------------------

- Incidence, nature, seriousness, severity and duration of adverse events and adverse device events in the 12 months following implantation of the ARGOS-IO pressure sensor.

Performance

- Limits of agreement between IOP measurements made using GAT and the ARGOS-IO system from V05 (day 30) through V11 (day 360).
- Incidence of device deficiencies in the 6 months following implantation
- Incidence of device deficiencies in the 12 months following implantation
- User acceptance of the implantation procedure by means of evaluation of the Implantation Procedure Questionnaire (Investigators)
- User acceptance of the ARGOS-IO system at the investigational site by means of evaluation of the Investigator Acceptance Questionnaire (Investigators)
- User acceptance of the ARGOS-IO system at home by means of evaluation of the Patient Acceptance Questionnaire (patients)
- Daily IOP self-measurement profiles (patients).

8.1.4 Equipment to be used to assess the clinical investigation variables and arrangements for monitoring maintenance and calibration

Sites will use their own ophthalmology diagnostic devices. The CRA will verify that the sites maintain and calibrate these devices on a regular basis.

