7.6.3	Ophthalmic examinations	24
8.	Special Statistical/Analytical Issues	25
8.1	Interim Analysis	25
8.2	Changes in the Planned Analysis	26
A.	APPENDICES	28
	List of Tables	28
	List of Figures	30
	List of Listings	31

List of Abbreviations and Key Terms

α	Type I error
ADE	Adverse Device Effect
AE	Adverse Event
ASIC	Application specific integrated circuit
ATC	Anatomical Therapeutic Chemical Classification
β	Type II error
CIP	Clinical Investigation Plan
DSMB	Data Safety Monitoring Board
FAS	Full-analysis-set
GAT	Goldmann Applanation Tonometry
HLT	High level term
HLGT	High level group term
IO	Intraocular
IOL	Intraocular lens
IOP	Intraocular Pressure
ITT	Intention to treat
LLT	Lowest level term
N	Sample number
OCT	Ophthalmic Coherence Tomography
p0	Proportion of patients in stage 1 with positive outcome
p1	Proportion of patients overall with positive outcome
POAG	Primary open angle glaucoma
PT	Preferred term
SADE	Serious Adverse Device Effect
SAE	Serious Adverse Event
SAP	Statistical Analysis Plan
SES	Safety evaluation set
SOC	System organ class
V	Visit

1. Introduction

This Statistical Analysis Plan (SAP) contains a more technical and detailed elaboration of the principal features of the statistical analyses described in the Clinical Investigation Plan Rev. G, date 05th January 2016, and includes planned detailed procedures for executing the statistical analysis of the primary and secondary variables and other data. The SAP is finalised and signed prior to hard lock of the database.

2. Study Design and Objectives

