2.4.2 Secondary Objectives

The secondary objectives of this clinical investigation are

- **Safety:** To evaluate the safety and tolerability of ARGOS-IO pressure sensor implantation between 3 and 12 months.
- **Performance:** To evaluate the performance of the ARGOS-IO system compared to GAT up to 12 months after implantation.

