6.5 Secondary Performance Variables

Assessment of the secondary performance variables include

- Limits of agreement between IOP measurements made using GAT and the ARGOS-IO system from Visit 10 through Visit 11
- Incidence of observed of device malfunctions in the 3, 6 and 12 months following implantation
- User acceptance of the implantation procedure by means of evaluation of the implantation procedure questionnaires (investigators)
- User acceptance of the ARGOS-IO system at the investigational site by means of evaluation of the investigator acceptance questionnaires (investigators)
- User acceptance of the ARGOS-IO system at home by means of evaluation of patient acceptance questionnaires (patients) at Visit 11
- Daily IOP self-measurement profiles (patients).

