8.2 Changes in the Planned Analysis

Departing from the planned analysis, the first DSMB meeting was conducted after 6 patients had completed Visit 4. The sponsor of this trial was enlightened that it is necessary to increase the overall sample size if this first DSMB meeting corresponds to a prepond analysis of the first stage of Simon's two stage design in order to maintain the type I and type II error. The report provided for this DSMB meeting comprised the listings and tables in the DSMB charter plus a table summarizing the compliance of subjects.

The second DSMB meeting was conducted after 11 patients completed Visit 5 (one month after implantation of the medical device). The report provided for this DSMB meeting comprised the listings and tables in the DSMB charter minus the summary of anterior segment examination results, posterior examination results, GAT measurements and ARGOS-IO measurements.

The first interim analysis independent from the DSMB was conducted after 21 subjects completed Visit 5 (one month after implantation of the medical device). The report provided comprised the listings and tables in the DSMB charter plus:

- Summaries of visual field and visual acuity results at screening and follow-up visits
- More detailed information about medical history, concomitant illnesses and previous/concomitant medications
- More detailed information about adverse events
- Additional summaries of GAT measurements and ARGOS-IO measurements including limits of agreement per visit and for all visits

The limits of agreement were provided in a separate document with corresponding table and figures. If multiple ARGOS-IO system measurements have been made at time points for which paired GAT/ARGOS-IO system measurements were to be compared, the mean of the replicate ARGOS-IO system measurements were used for agreement evaluation. Subsequently, this analysis was repeated by using the first replicate ARGOS-IO system measurement instead of the mean of the replicate measurements.

The second interim analysis independent from the DSMB was conducted after all subjects completed Visit 9 (6 months after implantation of the medical device). The report provided comprised the same tables and listings as the report for the interim analysis conducted after 21 subject completed Visit 5.

A. APPENDICES

List of Tables

Table 1	Disposition of patients (SES, FAS)
Table 2	Patient recruitment by month and by site
Table 3	Premature terminations

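### The SAP computes the secondary limits of agreement for V10–V11 only, whereas the supplied protocol defines them for V05–V11, and the supplied SAP text does not flag the difference

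*SAP*

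**What the plan says.** **Protocol.** The supplied protocol is Rev. C with an addendum. Section 8.1.3.2 gives the secondary performance endpoint as "Limits of agreement between IOP measurements made using GAT and the ARGOS-IO system from V05 (day 30) through V11 (day 360" and the synopsis says almost the same: "Limits of agreement between measurements made using GAT and the ARGOS-IO system from V05 (day 30) through V11 (day 360". The addendum text that is available does not touch this endpoint.

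**SAP.** Section 6.5 lists "Limits of agreement between IOP measurements made using GAT and the ARGOS-IO system from Visit 10 through Visit 11", and 7.5.1 repeats that window with day numbers ("Limits of agreement between IOP measurements made using GAT and the ARGOS-IO system from V10 (day 240) through V11 (day 360) will be assessed"). The MOVER 95% intervals in 7.5.1 belong to that window. Section 7.3 gives the primary limits, also with MOVER intervals, for V05–V09. The secondary performance objective in 2.4.2 is "To evaluate the performance of the ARGOS-IO system compared to GAT up to 12 months after implantation".

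**Outputs.** Tables 25 and 26 (limits for individual pairs, and over time) name no visit window. An overall display is mentioned in 7.3, 7.5.1 and the figure list, but only for plots, with no window or interval stated. Section 8.2 describes DSMB and interim reports and does not mention the secondary window. It does record that the first sponsor interim contained measurement summaries "including limits of agreement per visit and for all visits".

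**Version.** SAP section 1 says that the SAP elaborates "Clinical Investigation Plan Rev. G, date 05th January 2016". That revision was not supplied.

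**The concern.** The two documents describe different estimands under one endpoint label. The protocol's version summarises agreement over the whole period from first sensor use to one year. The SAP's version summarises late agreement only. If the SAP is followed as written, the final report will contain limits for V05–V09 and for V10–V11, but not the 12-month limits that the supplied protocol promises. A reader comparing report with protocol would find a named secondary endpoint missing and no explanation in the supplied SAP text. SAP 7.4, by contrast, does state openly that adverse device effects are tabulated differently from the protocol.

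The stake is limited. SAP 5.3 confines testing to the primary safety variable, and agreement is described without a margin. What is at issue is faithful reporting of a secondary endpoint and, to a lesser degree, its precision.

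**Working it through.** The plan gives no figure of its own here, so I counted the planned pairs and then compared interval widths.

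**1. Series per patient** (protocol 8.4.3.2: four series at V05, V07, V09 and V11; two at V06, V08 and V10). Each series gives one pair: the GAT reading and the mean of the ARGOS-IO replicates.

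| Window | Series per patient | × 22 patients | Share |
|---|---|---|---|
| V05–V09 (SAP primary) | 4+2+4+2+4 = 16 | 352 | 73% |
| V10–V11 (SAP secondary) | 2+4 = 6 | 132 | 27% |
| V05–V11 (protocol secondary) | 16+6 = 22 | 484 | 100% |

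**2. Where each window sits in time** (series-weighted mean of the nominal days):

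- V05–V09: (4×30 + 2×60 + 4×90 + 2×120 + 4×180)/16 = 1560/16 = 97.5
- V10–V11: (2×240 + 4×360)/6 = 1920/6 = 320
- V05–V11: (1560 + 1920)/22 = 3480/22 = 158.2

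The SAP's secondary limits are therefore centred about 162 days later than the protocol's (320 − 158.2 = 161.8).

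**3. Interval width for one limit.** Let the paired differences have between-patient variance B and within-patient variance W, with n = 22 patients and m pairs each. The documents give neither variance, so I scaled B + W = 1 and varied the between-patient share B from 0.1 to 0.9, assuming the same B and W in both windows.

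- Variance of a patient mean: S = B + W/m. Total variance: T = B + W = 1.
- MOVER bounds for T, where χ²(p; k) is the p-quantile with k degrees of freedom:
  - l = T − √{[S(1 − 21/χ²(0.975; 21))]² + [(1 − 1/m)W(1 − k/χ²(0.975; k))]²}
  - u = T + √{[S(21/χ²(0.025; 21) − 1)]² + [(1 − 1/m)W(k/χ²(0.025; k) − 1)]²}
  - k = 22(m − 1)
- Upper limit of agreement: mean + 1.96√T. Its interval extends
  - below by √{1.96²S/n + 1.96²(√T − √l)²}
  - above by √{1.96²S/n + 1.96²(√u − √T)²}

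Example, B = W = 0.5:

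- m = 6: S = 0.583, l = 0.745, u = 1.623. The interval extends 0.417 below and 0.625 above, width 1.04.
- m = 22: S = 0.523, l = 0.779, u = 1.549. The interval extends 0.379 below and 0.567 above, width 0.95.
- Ratio: 1.10.

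| Assumed between-patient share | Width, m = 6 | Width, m = 22 | Ratio |
|---|---|---|---|
| 0.1 | 0.67 | 0.43 | 1.55 |
| 0.3 | 0.85 | 0.69 | 1.22 |
| 0.5 | 1.04 | 0.95 | 1.10 |
| 0.7 | 1.24 | 1.19 | 1.04 |
| 0.9 | 1.45 | 1.43 | 1.01 |

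Widths are in units of the total SD of a paired difference; ratios are from unrounded widths. When patients differ mainly in their own systematic offset, the number of patients sets the precision and the window hardly matters. When within-patient scatter dominates, the shorter window costs up to about half as much width again.

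**4. Is the pooled estimate specified elsewhere?** I found no final-analysis section that gives V05–V11 limits with intervals. The all-visit limits in 8.2 belong to interim reports. The later of those was produced after Visit 9, so it could not be the complete 12-month estimate.

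**The case against.** The strongest reply is that Rev. C is the wrong benchmark. The SAP follows Rev. G and contains other material found in neither Rev. C nor the available addendum text: an interim analysis at 11–14 subjects with one month of follow-up, ultrasound biomicroscopy at screening and, in the same endpoint list, malfunctions at 3 months as well as 6 and 12. If Rev. G specifies V10–V11, the SAP is correct and 8.2 needs no entry. SAP 2.11 also sends adaptations that follow amendments to a document history, which is not in the supplied text. This stands. A reader might infer an undisclosed departure from the protocol, but the documents do not support that: the absence of a record can be stated only for the text supplied.

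A reader might also infer that data are dropped. They are not. V05–V09 and V10–V11 together cover every pair, both windows have MOVER intervals, and Listings 26 and 27 hold the ARGOS-IO and GAT measurements. A non-overlapping late window is a sensible summary in its own right, since 73% of the pooled pairs already enter the primary analysis. What remains is that two separate sets of limits are not the single set that the supplied protocol names.

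The objectives do not settle the matter. It is tempting to contrast the safety objective, "To evaluate the safety and tolerability of ARGOS-IO pressure sensor implantation between 3 and 12 months", with the performance objective and conclude that the latter must be cumulative. But SAP 6.4 evaluates safety cumulatively at 3, 6 and 12 months from implantation, so objective wording in this SAP does not map onto analysis windows.

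Finally, one might infer from the later centre of the V10–V11 window that its limits will be materially shifted by sensor drift. The only numerical drift rate that the protocol gives for this sensor in bench testing (5.1.1.1) is an upper bound below 3 mmHg per year, from six devices, which stabilised. That does not establish a shift in these patients.

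**Conclusion.** The mismatch is confirmed against the supplied protocol: V05–V11 there, V10–V11 in SAP 6.5 and 7.5.1, and no pooled 12-month limits with intervals specified for the final analysis. It is a minor reporting point, held with medium confidence because Rev. G and the SAP document history could not be seen. The main effect is a different estimand (late agreement instead of agreement over the year), based on 27% of the planned pairs. The precision cost ranges from negligible to about 55% more interval width. It rests on assumed variance shares, 22 patients with complete series, and variances that are the same in both windows. The primary performance analysis and the safety decision are not affected.

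**What to change.** 1. Compare SAP 6.5 and 7.5.1 with the secondary endpoint in protocol Rev. G.
2. Unless Rev. G changed the window, specify pooled V05–V11 limits of agreement with MOVER 95% intervals as the secondary endpoint, and keep V10–V11 as an added late summary.
3. If Rev. G did change the window, cite it in the SAP where the window is defined.
4. In either case, name the visit window in Tables 25 and 26. As a clerical correction, start the Bland-Altman plots in the figure list at Visit 05, because V02–V04 have GAT readings only.

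The cost is a few SAP sentences and at most one more run of an existing program, since limits for all visits were already produced at the interim analyses. No new data are needed.

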7.5.2 Device Malfunctions

Performance of the ARGOS-IO system after 3, 6 and 12 months will be assessed by means of incidence of observed device malfunctions. Number of device deficiencies as well as the number and relative frequency of patients reporting device deficiencies will be tabulated by event description.

7.5.3 Implantation Procedure Questionnaire

The acceptance of the implantation procedure will be assessed by the implantation procedure questionnaire, which is completed after surgery. Non free-text fields of the questionnaire will be summarised by absolute and percent frequencies (n, %). Free-text fields will be only displayed in listings.

7.5.4 Investigator Acceptance Questionnaire

The acceptance of the ARGOS-IO system by the investigator will be assessed by the user acceptance questionnaire, which is completed by the investigator at Visit 11. Non free-text fields of the questionnaire will be summarised by absolute and percent frequencies (n, %). Free-text fields will be only displayed in the listings.

7.5.5 Patients Acceptance Questionnaire

The acceptance of the ARGOS-IO system by patients at home will be assessed by the patient acceptance questionnaire, which is completed by the patient at Visit 11. Non free-text fields of the questionnaire will be summaries by absolute and percent frequencies (n, %). Free-text fields will be displayed in the listings only.

7.5.6 Self-measurement Patient Profiles

Measurements recorded by the patient will not be included into the evaluation of the FAS population.

7.6 Evaluation of Other Variables

7.6.1 Surgery and Lens Transplantation

Variables related to lens and surgery will be assessed using appropriate descriptive summary statistics for categorical data.

7.6.2 Complications during Surgery

Variables related to complications during surgery will be presented using absolute and relative frequencies (n, %).

7.6.3 Ophthalmic examinations

will be presented using standard descriptive statistics, i.e. summaries (n, mean, standard deviation, median, minimum and maximum) for quantitative variables and absolute as well as percent frequencies (n, %) for qualitative (i.e. categorical data).

8. Special Statistical/Analytical Issues

8.1 Interim Analysis

All 22 patients will be enrolled consecutively, until a serious adverse device effect (SADE) occurs. In that case, the DSMB will be called, and decides whether the enrollment can be continued or not.

An interim analysis will be performed after half of the study population (11-14 subjects) is enrolled with a minimum follow-up of 1 month. Another interim analysis to assess Safety and Performance will be performed, when all patients have completed the 3 month follow-up visit, the 6 month follow-up visit and every time an SADE occurs.

In order to take the principle of the two-stage design described by Simon into account, the trial will be terminated if more than 1 patient out of the first 11 patients enrolled experience at least one SADE during the first 3 months of the post-surgical follow-up period.

For the interim analyses, the report will comprise the following tables and listings specified in the DSMB charter from 3rd June 2014:

- Information on patient screening – number of screening failures
- Patient recruitment by month and by institution
- Eligibility violations
- Summary tables:
 - Baseline characteristics including
 - Date of informed consent signatures
 - Demographics (Age, Gender, Race)
 - Weight, Height
 - Anterior and posterior segment examination results and abnormalities
 - GAT measurement
 - Number of subjects with Adverse events by System Organ Class and Preferred terms
 - Serious adverse events
 - Adverse events
 - Device-related adverse events
 - Medical history (Year of Glaucoma diagnosis, Type of Glaucoma, Study Eye, Previous/concomitant illnesses, conditions and procedures)
 - Concomitant medications
 - Anterior and posterior examination results and abnormalities (follow-up visits)
 - Surgery documentation including
 - Complications

- Incision location
- Iridectomy
- IOL Implantation and location of the IOL haptics
- ARGOS-IO pressure sensor implantation and location of ASIC
- In situ position of IOL and ARGOS-IO implant at all relevant follow-up visits
- GAT measurements (V01, V02, V03, V04)
- GAT and ARGOS-IO serial measurements (V05, V06, V07)
- Protocol deviations
- Device Deficiencies, if any
- Unscheduled Visits, if any
- Premature termination of patients including date and reason
- Pregnancy reports, if any

8.2 Changes in the Planned Analysis

Departing from the planned analysis, the first DSMB meeting was conducted after 6 patients had completed Visit 4. The sponsor of this trial was enlightened that it is necessary to increase the overall sample size if this first DSMB meeting corresponds to a prepond analysis of the first stage of Simon's two stage design in order to maintain the type I and type II error. The report provided for this DSMB meeting comprised the listings and tables in the DSMB charter plus a table summarizing the compliance of subjects.

The second DSMB meeting was conducted after 11 patients completed Visit 5 (one month after implantation of the medical device). The report provided for this DSMB meeting comprised the listings and tables in the DSMB charter minus the summary of anterior segment examination results, posterior examination results, GAT measurements and ARGOS-IO measurements.

The first interim analysis independent from the DSMB was conducted after 21 subjects completed Visit 5 (one month after implantation of the medical device). The report provided comprised the listings and tables in the DSMB charter plus:

- Summaries of visual field and visual acuity results at screening and follow-up visits
- More detailed information about medical history, concomitant illnesses and previous/concomitant medications
- More detailed information about adverse events
- Additional summaries of GAT measurements and ARGOS-IO measurements including limits of agreement per visit and for all visits

The limits of agreement were provided in a separate document with corresponding table and figures. If multiple ARGOS-IO system measurements have been made at time points for which paired GAT/ARGOS-IO system measurements were to be compared, the mean of the replicate ARGOS-IO system measurements were used for agreement evaluation. Subsequently, this analysis was repeated by using the first replicate ARGOS-IO system measurement instead of the mean of the replicate measurements.

The second interim analysis independent from the DSMB was conducted after all subjects completed Visit 9 (6 months after implantation of the medical device). The report provided comprised the same tables and listings as the report for the interim analysis conducted after 21 subject completed Visit 5.

A. APPENDICES

List of Tables

Table 1	Disposition of patients (SES, FAS)
Table 2	Patient recruitment by month and by site
Table 3	Premature terminations
Table 4	Eligibility violations
Table 5	Demographics
Table 6	Anterior segment examination results (screening)
Table 7	Anterior abnormalities (screening)
Table 8	Posterior segment examination results (screening)
Table 9	Posterior abnormalities (screening)
Table 10	Anterior segment examination results (follow-up visits)
Table 11	Anterior abnormalities (follow up visits)
Table 12	Posterior segment examination results (follow-up visits)
Table 13	Posterior abnormalities (follow-up visits)
Table 14	Visual acuity (screening)
Table 15	Visual acuity (follow-up visits) – Subjective refraction
Table 16	Visual acuity (follow-up visits) – Objective refraction
Table 17	Visual acuity (follow-up visits) – ETDRS chart
Table 18	Visual acuity (follow-up visits) – Visual field
Table 19	GAT measurements (screening)
Table 20	Medical history by SOC and PT
Table 21	Medical history related to glaucoma
Table 22	Concomitant illnesses by SOC and PT
Table 23	Previous medication by ATC levels
Table 24	Concomitant medication by ATC levels
Table 25	Limits of agreement for individual measurement pairs
Table 26	Limits of agreement over time
Table 27	Device deficiencies
Table 28	Implantation procedure questionnaire
Table 29	Investigator acceptance questionnaire
Table 30	Patient acceptance questionnaire
Table 31	Complication during surgery
Table 32	Incision location
Table 33	Iridectomy
Table 34	IOL implantation
Table 35	ARGOS-IO implantation
Table 36	In-situ position
Table 37	Overall summary of AEs 3 month after implantation
Table 38	Overall summary of AEs 6 month after implantation
Table 39	Overall summary of AEs 12 month after implantation
Table 40	Number (%) of patients with AE and number of AE by SOC and PT 3 month after implantation
Table 41	Number (%) of patients with AE and number of AE by SOC and PT 6 month after implantation
Table 42	Number (%) of patients with AE and number of AE by SOC and PT 12 month after implantation
Table 43	Number (%) of patients with AEs by severity 3 month after implantation
Table 44	Number (%) of patients with AEs by severity 6 month after implantation
Table 45	Number (%) of patients with AEs by severity 12 month after implantation
Table 46	Number (%) of patients with AEs by causal relationship 3 month after implantation
Table 47	Number (%) of patients with AEs by causal relationship 6 month after implantation
Table 48	Number (%) of patients with AEs by causal relationship 12 month after implantation
Table 49	Number (%) of patients with ADEs and number of ADEs
Table 50	Serious AEs

Table 51 Serious AEs, listing of patients
Table 52 Serious ADEs, listing of patients
Table 53 Deaths, listing of all serious AEs of patients who died
Table 54 AEs leading to discontinuation

List of Figures

A detailed list of figures is not provided here. Planned figures are:

- Disposition of patients
- Bland-Altman plots of individual measurement pairs
- Bland-Altman plots over time (Visit 02 to Visit 11 plus overall)
- Bland-Altman plots for subgroups (if meaningful)

List of Listings

- Listing 1 Date of informed consent signatures
- Listing 2 Visit dates
- Listing 3 Unscheduled visits
- Listing 4 Premature discontinuation
- Listing 5 Screening failures
- Listing 6 Eligibility
- Listing 7 Allocation to analysis populations
- Listing 8 Demographics
- Listing 9 Anterior segment examination results
- Listing 10 Anterior abnormalities
- Listing 11 Posterior segment examination results
- Listing 12 Posterior abnormalities
- Listing 13 Visual acuity
- Listing 14 Visual field
- Listing 15 Medical history
- Listing 16 Medical history related to glaucoma
- Listing 17 Concomitant illnesses
- Listing 18 Previous medication
- Listing 19 Concomitant medication
- Listing 20 Complications during surgery
- Listing 21 Incision location
- Listing 22 Iridectomy
- Listing 23 IOL implantation
- Listing 24 ARGOS-IO implantation
- Listing 25 In-situ position
- Listing 26 ARGOS-IO serial measurements
- Listing 27 GAT measurements
- Listing 28 Protocol deviations
- Listing 29 Termination
- Listing 30 Pregnancy
- Listing 31 Implantation procedure questionnaire
- Listing 32 Investigator acceptance questionnaire
- Listing 33 Patient acceptance questionnaire
- Listing 34 Device deficiencies
- Listing 35 Unscheduled visits – overview
- Listing 36 Unscheduled visits – examinations and findings
- Listing 37 Adverse events
- Listing 38 Adverse device effects
- Listing 39 Serious adverse events
- Listing 40 Adverse events leading to discontinuation
- Listing 41 Deaths
